## 6.4 STUDY INTERVENTION/EXPERIMENTAL MANIPULATION ADHERENCE

Both local and global adherence will be measured. Local adherence will be the percent of completed versus expected activities in each of the available categories (i.e., ((# completed/# expected) x 100%)), including: self-monitoring, activity levels, reading psychoeducational materials, problem solving, etc.). Global adherence will be measured with a similar calculation for virtual attendance/contact with scheduled coach check-ins.

## 6.5 CONCOMITANT THERAPY

N/A

### 6.5.1 RESCUE THERAPY

N/A

## 7 STUDY INTERVENTION/EXPERIMENTAL MANIPULATION DISCONTINUATION AND PARTICIPANT DISCONTINUATION/WITHDRAWAL

### 7.1 DISCONTINUATION OF STUDY INTERVENTION/EXPERIMENTAL MANIPULATION

All participants will be contacted to complete all follow-up assessments unless they indicate that they would like to be withdrawn from the study. Participants are instructed in the consent form to contact the research staff directly if they would like to withdraw. Participants may indicate that they would like to withdraw from the intervention, but are still willing to complete future follow-up assessments. Contacts made to these participants will be assessment-related and not intervention-related. Depending on when the participant withdraws and under which circumstances would dictate the remaining procedures that they complete. Research staff will attempt to collect the reason for discontinuing at the time of withdrawal.

### 7.2 PARTICIPANT DISCONTINUATION/WITHDRAWAL FROM THE STUDY

Participants are free to withdraw from participation in the study at any time upon request.

An investigator may discontinue a participant from the study for the following reasons:

- The study is being stopped
- Significant study intervention non-compliance
- Lost-to-follow up; unable to contact participant
- Any event, medical condition or situation occurs such that continued collection of follow-up study data would not be in the best interest of the participant or might require an additional treatment that would confound the interpretation of the study
- Currently breastfeeding or pregnant (withdraw from intervention, but will still complete follow-up surveys)

Should someone report that they are breastfeeding or pregnant, we will stop the intervention (aka withdraw from intervention). They will not receive any further intervention content. We will still ask if they'd be willing to complete surveys until the end of their 2.5-year participation as this would pose no harm the mother or fetus.

The reason for participant discontinuation or withdrawal from the study will be recorded in the tracking form in REDCap. Participants who are randomized and subsequently withdraw or are discontinued from the study, will not be replaced.

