### 9.3 POPULATIONS FOR ANALYSES

All analyses will be intent to treat (include all randomized participants). Sensitivity analyses will include examining sources of missing data and alternative parameter estimates under different assumptions of missing data (e.g., missing completely at random, missing at random, multiple imputation).

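### Section 7.2 permits follow-up to end because a confounding treatment might be needed, which conflicts with 7.1 and fits badly with intent to treat in 9.3, and added treatment is not captured

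*Combined protocol and SAP*

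**What the plan says.** Section 7.2 opens its list with "An investigator may discontinue a participant from the study for the following reasons". One reason covers any event, condition or situation in which further data collection would be against the participant's interest, or which "might require an additional treatment that would confound the interpretation of the study". Another reason is "Significant study intervention non-compliance". Only the entry on pregnancy and breastfeeding separates stopping the intervention from leaving the study: "withdraw from intervention, but will still complete follow-up surveys". The section adds: "The reason for participant discontinuation or withdrawal from the study will be recorded in the tracking form in REDCap".

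Section 7.1 sets a different default: "All participants will be contacted to complete all follow-up assessments unless they indicate that they would like to be withdrawn from the study". Section 9.3 states: "All analyses will be intent to treat (include all randomized participants"). Its examples of alternative missing-data assumptions are missing completely at random, missing at random (MAR) and multiple imputation. Section 9.4.2 assumes MAR for the initial model.

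Section 6.5, headed "CONCOMITANT THERAPY", contains only N/A, as does 6.5.1 on rescue therapy. Neither the Schedule of Activities (1.3) nor the follow-up assessment list in 4.1 has an item on other weight treatment. Health care practices and utilization appear only among the baseline measures (1.1 and 2.1).

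**The concern.** Participants have a BMI above 27 and want to lose weight. The intervention ends at 12 months and follow-up runs to 30. In that setting, a treatment that would confound the study plausibly includes a weight-loss drug, surgery or another programme. Needing one can follow from poor response, and so from the assigned arm. A rule that allows follow-up to stop for this reason may discard later weights on a ground related to the outcome. The trigger is only that treatment might be needed, and the decision is discretionary. Participants are unblinded (6.3), and blinding of staff is not described.

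There is a second gap. A participant who starts another treatment and stays in the study contributes weights that include its effect, and nobody can identify those weights. The 6- and 12-month contrasts and the later follow-up could therefore mix two kinds of participant: some whose later weights are missing and inferred, and some whose weights carry an unrecorded treatment effect. The plan has no means of separating them.

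**Working it through.** **The passages side by side**

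- Section 7.1 follows everyone, with one exception: the participant's own request to withdraw.
- Section 7.2 adds exits chosen by the investigator, and these are exits from the study. The entry at issue itself speaks of continued collection of follow-up data, so ending collection is what it contemplates.
- The pregnancy and breastfeeding entry shows that the plan can separate stopping the intervention from stopping follow-up. The confounding-treatment and non-compliance entries do not make that separation.
- Section 9.3 keeps all randomised participants in the analysis. Someone discontinued under 7.2 stays in the model through earlier weights, but later weights are inferred under MAR.

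**The plan's own figures, used here only as yardsticks**

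Section 9.2 gives 85% power at 24 months for a BMI-change difference of 1.2 (SD 4.5, N = 600, 30% missing). A cross-sectional check uses 300 x 0.7 = 210 per arm and an assumed alpha of 0.05.

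- Unadjusted power is 0.780 two-sided and 0.862 one-sided.
- Two-sided with baseline adjustment, it is 0.817 (correlation 0.3) to 0.884 (correlation 0.5).

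The stated 85% lies within this range. Alpha, sidedness and the growth covariances are not given, so the simulation can be neither reproduced nor called wrong. The other yardstick is the within-treatment difference of 0.8.

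**Possible size**

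Let qC and qT be the shares removed in control and Noom Health. Let D be the further BMI loss that the removed would have shown beyond what the model infers for them, taken as equal in both arms. The true mean loss in an arm is then the inferred mean plus q x D, so the estimated Noom Health advantage is off by

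(qC - qT) x D.

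The documents give none of these inputs. All are assumed.

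| qC | qT | D (BMI units) | Shift | Share of 0.8 | Share of 1.2 |
|---|---|---|---|---|---|
| 5% | 5% | any | 0 | 0% | 0% |
| 5% | 2% | 1 | 0.03 | 4% | 2.5% |
| 4% | 2% | 2 | 0.04 | 5% | 3% |
| 10% | 5% | 4 | 0.20 | 25% | 17% |
| 15% | 5% | 3 | 0.30 | 38% | 25% |
| 15% | 5% | 5 | 0.50 | 63% | 42% |
| 5% | 10% | 4 | -0.20 | -25% | -17% |

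The sign is open. With more removals in control, the advantage is overstated if the unseen weights would have included the benefit of added treatment (D positive). It is understated if the removed would have done worse than the model infers (D negative). Reversing the arms reverses both. If D differs by arm, the shift is qC x DC - qT x DT, so equal shares alone do not guarantee zero.

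**Effect on power**

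Take removals of 2% and 5% up to 5% and 15% on top of the 30% missing. Two-sided unadjusted power falls from 0.780 to between 0.766 and 0.736 from lost numbers alone. If a shift of 0.03 to 0.30 also shrinks the 1.2 difference, it falls to between 0.744 and 0.494.

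**The case against.** Several points on the other side stand.

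- A reader might infer that the reason for removal cannot be analysed. Section 7.2 contradicts that, because the reason goes into REDCap. What is missing is the added treatment itself and any planned use of the logged reason.
- A reader might infer that weights are in fact removed selectively. The rule says may. No rate, no difference between arms and no intention to use it this way is documented.
- The entry does not mention poor response or weight treatment. Reading it that way is plausible in this population, but it is an inference.
- Section 7.1 may be the operating default, in which case follow-up would continue. The documents do not establish that data collection ends. They establish that the two sections disagree.
- Earlier weights remain in the growth model. If removal depends only on weights already observed, MAR covers it. Bias needs dependence on unseen values beyond that history.
- The 0.2 figure compares removing all such participants with keeping all of them, whereas a discretionary rule would remove only some. Comparing it with 0.8 also assumes that the full 4 units are realised within the treatment period.

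These points limit the claim but do not remove it. The conflict between 7.1 and 7.2 is on the page, and the logged reason says nothing about added treatment in those who stay.

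**Conclusion.** The concern holds as a defect in the rule and a gap in data capture. It is not a demonstrated bias. Section 7.2 permits follow-up to end for a post-randomisation reason plausibly linked to response and arm. That conflicts with 7.1 and sits badly with the intent-to-treat plan. Added treatment is not recorded, and no named sensitivity analysis covers informative removal.

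The size cannot be fixed from the documents. The 0.2 BMI units rest wholly on the assumed 10% against 5% and 4 units. Zero and the opposite sign are equally compatible with the text. The stronger readings, that outcomes are being deleted or that intent to treat is broken outright, are not supported. The point still merits action: weights that are not collected cannot be recovered by later analysis, and the remedy is cheap.

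**What to change.** 1. Reconcile 7.1, 7.2 and 9.3. Neither possible need for a confounding treatment nor intervention non-compliance should be a ground for ending collection of weights and questionnaires. Collection would end only if consent is withdrawn or if continuing it is against the participant's interest.
2. Replace the N/A in 6.5 with one REDCap item at the remaining visits, covering any other weight-loss treatment started since randomisation, with type and start date. Ask it retrospectively: the note in 5.2 shows that recruitment has closed, so some visits, possibly including 6 and 12 months, may be past.
3. State in 9.3 that the primary analysis uses all observed weights regardless of added treatment.
4. Add one supplementary analysis that sets weights after the recorded start to missing and imputes them by arm.

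The cost is amendment wording, one question at existing visits and one extra analysis. The downside is that the primary contrast then includes the effects of added treatment. Recalled dates will be imperfect, and weights already forgone stay lost. These changes concern data collection and analysis only. No clinical rule is proposed.

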### 7.3 LOST TO FOLLOW-UP

Participants will be considered lost to follow-up if they withdraw from the study by directly contacting our research team or if they don't complete the follow-up assessments. Participants will be contacted

throughout the assessment window via phone, email, and the family/friend contact. If no contact is made during the assessment window, they will be deemed lost to follow-up.

## 8 STUDY ASSESSMENTS AND PROCEDURES

### 8.1 ENDPOINT AND OTHER NON-SAFETY ASSESSMENTS

Noom Coaches will be trained to monitor the safety of their participants. Additionally, in the introductory material given to all participants, information about how to identify and report a crisis will be outlined. This is to safeguard participants in the event there is a problem with the facilitator. Since this is a non-clinical population (obese individuals without serious psychopathology) and Noom has never had any incidents with their typical overweight population, we do not anticipate this will be a problem. In the event a Coach discovers one of their group members has a serious psychiatric condition (e.g., severe eating disorder, substance dependence), he/she will be instructed to alert Noom and Mt. Sinai immediately via a shared e-mail address (e.g., [[contact]](mailto:[contact])). These incidents will be dealt with on a case-by-case basis and the absolute minimal course of action will be to contact the identified participant with relevant psychoeducational material and/or information about where they can go to receive help.

Within the context of the present study, Serious Adverse Events (SAEs) include any serious decline of psychological functioning (e.g., suicidal ideation, plan, or action) that requires immediate psychiatric intervention (e.g., inpatient hospitalization). This may occur while participants are in the assessment or follow-up components of the study. Important medical events that may not result in death, be life-threatening, or require hospitalization may be considered serious adverse experiences when, based on appropriate medical judgement of the study physician, they may jeopardize the patient or subject and may require medical or surgical intervention to prevent one of the outcomes in this definition. The judgement of whether a particular AE meets the above criteria for an SAE for the proposed study will be determined by the PI. It will also be the PI's responsibility to manage all SAEs and to make referrals for appropriate care as necessary.

### 8.2 SAFETY ASSESSMENTS

N/A. There are no formal safety assessments performed in this protocol. If an adverse event is reported to the research team, we will follow-up as needed depending on the severity of the event and relation to the study.

### 8.3 ADVERSE EVENTS AND SERIOUS ADVERSE EVENTS

#### 8.3.1 DEFINITION OF ADVERSE EVENTS

The intervention in this trial is low risk and is not expected to result in adverse events. Expected risks they may occur include anxiety related to eating or change in weight status or emotional discomfort during assessments. An adverse event will be defined as any untoward medical occurrence related to the intervention.

### 8.3.2 DEFINITION OF SERIOUS ADVERSE EVENTS

A serious adverse event in this project will be defined as an adverse event that occurs during participation that is unanticipated, related to the research, and serious in nature (seriousness as defined by hhs.gov -- <https://www.hhs.gov/ohrp/sites/default/files/ohrp/policy/advevntguid.pdf>)

### 8.3.3 CLASSIFICATION OF AN ADVERSE EVENT

#### 8.3.3.1 SEVERITY OF EVENT

Adverse events will be classified on the following categories by research staff. All events will be brought to the attention of the PI, who will also confirm severity.

- **Mild** – Events require minimal or no treatment and do not interfere with the participant's daily activities.
- **Moderate** – Events result in a low level of inconvenience or concern with the therapeutic measures. Moderate events may cause some interference with functioning.
- **Severe** – Events interrupt a participant's usual daily activity and may require systemic drug therapy or other treatment. Severe events are usually potentially life-threatening or incapacitating. Of note, the term "severe" does not necessarily equate to "serious".]

#### 8.3.3.2 RELATIONSHIP TO STUDY INTERVENTION/EXPERIMENTAL MANIPULATION

Adverse events will be assessed to determine relation to the intervention. Determinations will be made by research staff. All events will be brought to the attention of the PI, who will also confirm relation to study.

- **Definitely Related** – There is clear evidence to suggest a causal relationship, and other possible contributing factors can be ruled out. The clinical event, including an abnormal laboratory test result, occurs in a plausible time relationship to study procedures administration and cannot be explained by concurrent disease or other drugs or chemicals. The response to withdrawal of the study procedures should be clinically plausible. The event must be pharmacologically or phenomenologically definitive.
- **Probably Related** – There is evidence to suggest a causal relationship, and the influence of other factors is unlikely. The clinical event, including an abnormal laboratory test result, occurs within a reasonable time after administration of the study procedures, is unlikely to be attributed to concurrent disease or other drugs or chemicals, and follows a clinically reasonable response on withdrawal.

- **Potentially Related** – There is some evidence to suggest a causal relationship (e.g., the event occurred within a reasonable time after administration of study procedures). However, other factors may have contributed to the event (e.g., the participant's clinical condition, other concomitant events). Although an AE may rate only as "possibly related" soon after discovery, it can be flagged as requiring more information and later be upgraded to "probably related" or "definitely related", as appropriate.
- **Unlikely to be related** – A clinical event, including an abnormal laboratory test result, whose temporal relationship to study procedures administration makes a causal relationship improbable (e.g., the event did not occur within a reasonable time after administration of the study procedures) and in which other drugs or chemicals or underlying disease provides plausible explanations (e.g., the participant's clinical condition, other concomitant treatments).
- **Not Related** – The AE is completely independent of study procedures administration, and/or evidence exists that the event is definitely related to another etiology. There must be an alternative, definitive etiology documented by the clinician.]

#### 8.3.3.3 EXPECTEDNESS

Research staff will be responsible for determining whether an adverse event is expected or unexpected. An AE will be considered unexpected if the nature, severity, or frequency of the event is not consistent with the risk information previously described for the study procedures. All events will be brought to the attention of the PI, who will also confirm expectedness.

#### 8.3.4 TIME PERIOD AND FREQUENCY FOR EVENT ASSESSMENT AND FOLLOW-UP

The occurrence of an adverse event (AE) or serious adverse event (SAE) may come to the attention of research staff during the study.

All AEs, not otherwise precluded per the protocol, will be captured on the appropriate tracking form in REDCap. Information to be collected includes event description, time of onset, assessment of severity, relationship to study procedures, and time of resolution/stabilization of the event. All AEs occurring while on study will be documented appropriately regardless of relationship. All AEs will be followed to adequate resolution.

Any medical or psychiatric condition that is present at the time that the participant is screened will be considered as baseline and not reported as an AE. However, if the study participant's condition deteriorates at any time during the study, it will be recorded as an AE.

#### 8.3.5 ADVERSE EVENT REPORTING

As described in the prior Ideate protocol, there is no DSMB required for this project. All adverse events will be brought to the attention of the project manager immediately. The PI will be made aware of events within 24 hours. The IRB will be notified of non-serious events at the time of annual renewal.

### 8.3.6 SERIOUS ADVERSE EVENT REPORTING

Serious adverse events will be brought to the attention of the project manager immediately. The PI will be made aware of events within 24 hours. The IRB will be notified of serious events within 2 business days and the funding agency will be notified of serious events within 5 business days.

### 8.3.7 REPORTING EVENTS TO PARTICIPANTS

N/A

### 8.3.8 EVENTS OF SPECIAL INTEREST

N/A

### 8.3.9 REPORTING OF PREGNANCY

Participants reporting that they are pregnant will be withdrawn from the intervention, but may still complete the follow-up surveys.

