## 1.2 SCHEMA

**Flow Diagram (randomized controlled trial)**

### 1.3 SCHEDULE OF ACTIVITIES

The schedule of activities (SOA) provided below outlines the expected activities for each research visit. Participants are expected to be enrolled in the study for 2.5 years and complete all research visits via a HIPAA compliant video platform (Zoom) and REDCap.

	Pre-screening (Pre-consent)	Visit 1 Day 1	Visit 2 Day 30 ± 42	Visit 3 Day 121 ± 42	Visit 4 Day 182 ± 42	Visit 5 Day 365 ± 42	Visit 6 Day 547 ± 42	Visit 7 Day 730 ± 42	Visit 8 Day 912 ± 42
EMR Review Eligibility	X								
Informed Consent		X							
Demographics		X							
Height, Weight,		X	X	X	X	X	X	X	X
Outcome Evaluation									
Depression, Anxiety, Stress Scale		X	X	X	X	X	X	X	X
Quality of Life Questionnaire		X	X	X	X	X	X	X	X
ASA24		X	X	X	X	X	X	X	X
Eating Disorder Examination Questionnaire		X	X	X	X	X	X	X	X
International Physical Activity Questionnaire		X	X	X	X	X	X	X	X
PROMIS Sleep Impairment		X	X	X	X	X	X	X	X
Short Form Health Survey		X	X	X	X	X	X	X	X

Brief Self-Efficacy Scale for Healthy Eating		X	X	X	X	X	X	X	X	X
Randomization		X								
Control & Experimental Interventions – Noom App vs Digital Control		X	X	X	X	X				
Adverse Events Reporting		X	X	X	X	X	X	X	X	X

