Noom Digital Health participants will use a limited version of Noom for 6 months of intervention and 6 months of maintenance (12 months total). The features include diet, physical activity, and weight tracking. Weight loss advice will be given once a week. Participants will use the app multiple times per day to log eating episodes (the number of episodes will vary by person). the app for 6 months after intervention to maintain weight loss, with goal to maintain weight.

Acceptability/Satisfaction assessments: During the intervention, we will send a 7-point Likert-type scale at monthly intervals Noom Health participants to assess satisfaction with the Noom app. For those in the Noom Digital Health condition, we will give a one question assessment at the same time points to indicate participants are still enrolled in research procedures.

Follow-up visits (1 month, 4 months, 6 months, 12 months, 18 months, 24 months, and 30 months): 24-hour dietary recall interview, EDE-Q, Q-LES-Q-SF, IPAQ, Brief Self-Efficacy Scale for Healthy Eating, DASS, SF-36, PROMIS, Demographics and Smartphone Comfort.

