#### 5.2 EXCLUSION CRITERIA

- Contraindication to smartphone use (e.g., seizures from prior smartphone use, do not own a smartphone).

- Acute suicide risk
- Pregnancy
- Current and planned breastfeeding\*

Individuals who are pregnant should not participate in a medically unsupervised weight loss program due to the risks associated.

\* Added after recruitment closed

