##### 10.1.1.2 CONSENT PROCEDURES AND DOCUMENTATION

Prior to the consent call, interested individuals will be sent a REDCap link to the electronic version of the full-study consent form. Informed consent and screening interviews will be conducted via a HIPAA-compliant videoconference (Zoom). A member of the study staff will review the study protocol and obtain written informed consent using the full-study e-consent form. Voluntary written informed consent will be completed prior to completing study procedures in accordance with the PPHS of Mount Sinai. The consent process includes a description of the remaining screening procedures and assessments, treatment, and other study requirements and will be obtained in a closed office with only members of the research group present. No reference to the potential subject's identity will be made outside of closed quarters. The consent form includes an explanation of study procedures, their time commitments, risks and benefits, alternatives to participation, the confidentiality of information, and the rights of research subject. Participants will be given the opportunity to have all their questions answered. Participants' understanding of the protocol will be examined by direct questioning prior to their signing the consent forms. The potential subject will provide their e-signature and name as well as the date of the consenting process on the e-consent form. After the subject submits the form, the study staff member obtaining the consent will provide their signature, name, and the consenting date on the signed e-consent form and send a copy of the form to the participant via an encrypted email. All study related questions from study

participants that a research staff member is unable to address will be referred to the Principal Investigator or other co-investigators. No further information will be gathered until participants have provided written, signed informed consent.

The consent form will explicitly notify participants that participation is voluntary, can be discontinued at any time and will not affect their medical care or status in the Mount Sinai Health System. Patients will be screened to ensure they do not meet criteria for exclusion.

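### Pregnancy or breastfeeding stops the intervention only when a participant reports it, and the protocol describes no question about either state after entry

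*Combined protocol and SAP*

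**What the plan says.** Section 5.2 (Exclusion Criteria) excludes pregnancy and gives the reason: "Individuals who are pregnant should not participate in a medically unsupervised weight loss program due to the risks associated". It also lists current and planned breastfeeding, with a footnote: "Added after recruitment closed".

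Two later sections act on these states during the trial. Section 7.2: "Should someone report that they are breastfeeding or pregnant, we will stop the intervention (aka withdraw from intervention". Section 8.3.9, on pregnancy alone: "Participants reporting that they are pregnant will be withdrawn from the intervention, but may still complete the follow-up surveys". Section 7.2 places the same states in a list of reasons for which an investigator may discontinue a participant, and then says in the text below that the intervention will be stopped.

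On checking, Section 10.1.1.2 promises a screen at consent: "Patients will be screened to ensure they do not meet criteria for exclusion". In the Schedule of Activities (Section 1.3) the row "EMR Review Eligibility" is marked before consent only. Section 4.1 gives the content of the follow-up visits: "24-hour dietary recall interview, EDE-Q, Q-LES-Q-SF, IPAQ, Brief Self-Efficacy Scale for Healthy Eating, DASS, SF-36, PROMIS, Demographics and Smartphone Comfort". The monthly contact in Section 4.1 is a satisfaction rating in the Noom Health arm. In the Noom Digital Health arm, "we will give a one question assessment at the same time points", to show that the person is still enrolled. Section 8.2 says that no formal safety assessments are made.

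**The concern.** The protocol names a state in which people should not be exposed to the programme and has a step for ending the exposure, but that step waits for the participant to speak. Someone who becomes pregnant and does not think to tell the study, or does not know that she should, keeps receiving weight-loss content. For breastfeeding the gap starts at entry, because the criterion was not in force while people were being enrolled.

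There is also a data consequence. Weight is a primary outcome, Section 9.3 analyses everyone randomised, and no section says how weights taken during pregnancy are identified or handled.

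**Working it through.** The documents give no figure for detection or exposure time, so there is none to reproduce. The check is a search of each place where a question could sit, followed by arithmetic on the visit days.

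**Where could either state be picked up after entry?**
- Schedule of Activities (1.3): no row for pregnancy or breastfeeding.
- Follow-up list (4.1) and source records (10.1.9.1): named questionnaires, app data, and height and weight. Neither state is mentioned.
- Monthly contact (4.1): satisfaction in one arm, enrolment status in the other.
- Adverse event row (1.3), marked at every visit: Section 8.3.1 confines an adverse event to an untoward occurrence related to the intervention, whereas Section 8.3.4 records events whatever their relationship. Even on the wider wording, 8.3.4 speaks of events that come to staff attention and describes no question about these states.
- Coaches (6.2.1): trained to watch safety, with serious psychiatric conditions as the worked case and no pregnancy query named. Coach access is a listed feature of Noom Health only (4.1), so chance detection may differ between arms.
- Entry screen (5.2, 10.1.1.2): cannot find a later pregnancy, and could not apply a breastfeeding criterion that did not yet exist.

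**How long could exposure run as written?** Section 6.1.2 sets 6 months of intervention plus 6 of maintenance, and Visit 5 is at Day 365. With no question described, the visit spacing limits nothing. The ceiling is the length of the intervention:

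365 − 1 = 364 days, or 364 / 30.4375 = 12.0 months.

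A single pregnancy is shorter than this. Breastfeeding already under way at entry, or pregnancy followed by breastfeeding, could fill it.

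**What would asking achieve?** If both states were asked about at every visit, the longest unseen interval during the intervention would be Visit 4 (Day 182 ± 42) to Visit 5 (Day 365 ± 42):
- nominal: 365 − 182 = 183 days
- shortest: (365 − 42) − (182 + 42) = 323 − 224 = 99 days
- longest: (365 + 42) − (182 − 42) = 407 − 140 = 267 days

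The nominal gaps before that are 29, 91 and 61 days. If the monthly contact carried the item as well, the interval would be about one month, provided the contact is answered and runs for all 12 months.

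**The case against.** The strongest reply is that the documents list instruments and not their items. The consent form and the REDCap forms are not in them. Section 4.1 repeats a demographics form at follow-up whose content cannot be seen (the Schedule of Activities marks demographics at Visit 1 only). Visits are live video calls with an observed weight, adverse events are a standing row, and Noom Health participants talk to coaches. This stands in part: the supportable statement is that no question is described, not that none is asked. But if the consent form tells participants to report, detection still depends on their volunteering it.

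It is also fair that the remaining benefit is unknown. Recruitment has closed, and the documents do not say how many participants are still within their 12 months.

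A reader might go further in four ways that the documents do not support.
- *That exposure is bounded by the six-month gap between Visits 4 and 5.* That gap would matter only if the visits asked.
- *That a number of affected participants can be given.* The documents have no pregnancy rate, no sex split and no non-reporting fraction.
- *That the weight comparison is badly distorted.* One person's gain is not comparable with the planned mean BMI difference of 0.8 within treatment, because each affected person moves an arm mean by only 1/300 of her own shift. Even on deliberately high assumptions, none of them from the documents (17 affected, all in one arm, each 3.7 BMI units higher at the same visit), the arm mean moves by 17 × 3.7 / 300 = 0.21. With pregnancies balanced by randomisation, the effect on the difference would cancel in expectation.
- *That planned breastfeeding in Section 5.2 contradicts current breastfeeding in Section 7.2.* An entry criterion can look ahead while a withdrawal criterion acts on a present state.

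**Conclusion.** The point holds as a participant-protection gap that is cheap to close. The sponsor's own stopping rule depends on volunteered reports, and no described procedure prompts one after entry. Followed as written, an unreported state could continue on the app for up to about 364 days. This rests on two assumptions: that the forms outside the documents contain no such item, and that the participant stays on the app for the full 12 months. How many people are affected cannot be estimated from the documents.

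The effect on the primary analysis is secondary and probably small. It cannot be checked unless dates are recorded, and finding a pregnancy does not by itself settle how the weights are analysed, since Section 9.3 keeps everyone in.

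Separately, Section 7.2 says both that an investigator may discontinue for these states and that the intervention will be stopped, and Section 8.3.9 leaves out breastfeeding. These passages must be reconciled. What the rule should be is for the sponsor.

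**What to change.** 1. Add one yes/no item on current pregnancy or breastfeeding, with start and end dates, to the existing REDCap visit forms at every visit in both arms, and show it in the Schedule of Activities.
2. Add the same item to the existing monthly contact in both arms, and state that this contact continues to month 12. Identical wording keeps detection from depending on coach access.
3. Route a yes to the withdrawal step already in Section 7.2. No new clinical rule is needed.
4. Ask current participants once when the amendment takes effect, since the breastfeeding criterion came after enrolment.
5. In Section 9.3 or 9.4.2, keep the intent-to-treat analysis as primary and add a sensitivity analysis in the same set that uses the dates to flag affected weights, for example by setting them to missing and refitting the growth model.
6. Reconcile the permissive and mandatory wording in Section 7.2 with each other and with Section 8.3.9.

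If the forms already carry such an item, the protocol need only say so, and items 5 and 6 remain.

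The cost is one extra question and a short amendment, with no new visits. Some participants will come off the intervention who would otherwise not have been identified. The safety benefit is confined to those still within their 12 months; for the others, visits run to Day 912, so the dates still serve to flag weights.
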